7.22 Expansion Portion

The Expansion portion of this trial will commence for Arms A and B as soon as the Safety portions for BOTH arms are completed. The MTD/ Expansion cohort dose can be different for Arm A and B.

Table 7.22: Dose for Expansion cohort

Agent	Dose	Route	Day(s)	ReRx
AraC ¹	20 mg	SC twice daily	1-5 & 8-12 ²	Every 28 days
AZD1775	MTD (from escalation portion)	PO once daily	1-5& 8-12 ²	Every 28 days

¹ AraC dose is a fixed dose of 20 mg s.c. per a single dose twice daily.

²AZD1775 should be taken either 2 hours before or 2 hours after a meal.

7.3 Treatment Plan for AZD1775 single agent (Arm C)

7.31 Safety Portion

The Safety portion of this trial will treat and monitor up to six subjects in the arm and observe them for a minimum of 21 days to assess toxicities. The Safety portion will first treat 3 patients at a single dose AZD1775 of 300mg daily (dose level 0) on days 1-5 and 8-12 for 21 days. If 0/3 patients experience DLT, another 3 patients will be treated. If \leq 1/6 patients have DLT, 300mg will be the tolerated dose (MTD) and advanced to the Expansion portion of the study. If \leq 2/6

patients have DLT, dose will be de-escalated to dose level -1 (AZD1775 250mg daily on days 1-5 and 8-12 for 21 days) and 3 patients treated. If $\leq 1/3$ patients have DLT another 3 patients will be treated. If $\leq 1/6$ patients have DLT, 250 mg AZD1775 will be the tolerated dose (MTD) and advanced to the Expansion portion of the study. If $\leq 2/6$ patients have DLT at dose level -1 (250 mg AZD1775) dose will be further de-escalated to dose level -2 (AZD1775 200mg daily on days 1-5 and 8-12 for 21 days) and 3 patients treated. If $\leq 1/3$ patients have DLT another 3 patients will be treated. If $\leq 1/6$ patients have DLT, dose level -1 (200 mg AZD1775) will be the tolerated dose (MTD) and advanced to the Expansion portion of the study. If $\leq 2/6$ patients have DLT at dose level -2 (200 mg AZD1775) dose will be further de-escalated to dose level -3 (AZD1775 150 mg daily on days 1-5 and 8-12 for 21 days) and 3 patients treated. If $\leq 1/3$ patients have DLT another 3 patients will be treated. If $\leq 1/6$ patients have DLT, dose level -3 (150 mg AZD1775) will be the tolerated dose (MTD) and advanced to the Expansion portion of the study. If $\leq 2/6$ patients have DLT at dose level -3 (150 mg AZD1775) **or** if $\geq 2/6$ patients experience DLT at any dose level, then enrollment into that dose level will be placed on hold, and a meeting of all participating investigators, the NYU DSMC Medical Monitor, the Astra Zeneca Trial/ Program Lead will be called to determine how best to proceed, as well as available PK data will be reviewed.

Table 7.31 Single agent AZD1775 (Arm C)

Dose	AZD1775 ¹
0	300 mg PO once daily days 1-5 & 8-12 every 21 days
-1	250 mg PO once daily days 1-5 & 8-12 every 21 days
-2	200 mg PO once daily days 1-5 & 8-12 every 21 days
-3	150 mg PO once daily days 1-5 & 8-12 every 21 days

¹AZD1775 should be taken either 2 hours before or 2 hours after a meal.

7.32 Expansion Portion

The Expansion portion of this trial will commence for Arm C as soon as the Safety Portion is completed.

Starting Dose

Agent	Dose	Route	Day(s)	ReRx
AZD1775 ¹	MTD	PO once daily	1-5 & 8-12,	Every 21 days

1AZD1775 should be taken either 2 hours before or 2 hours after a meal.

7.33 Hydroxyurea (HU)

For patients randomized to Arm C single agent AZD1775, HU may be added after the first cycle of therapy at the physicians discretion after discussion with the PI. HU dose should be started according to clinical judgement at 500-1000mg/ day and titrated for additional myelosuppression as needed. Note: for patients with Myelofibrosis, HU can be given during cycle 1 at the previously tolerated dose.

7.4a Toxicity Assessment for Safety Portion: DLT definition and RP2D

Toxicity will be measured per NCI-CTCAE version 5.0. DLT is defined as an adverse event occurring during the first cycle of treatment that is not clearly related to the subject's underlying disease and that meets one of the following:

- Grade 3 or higher toxicity as per NCI Common Terminology Criteria for Adverse Events (CTCAE) version 5.0 not clearly resulting from the underlying leukemia and that does not resolve to \leq Grade 2 within 24 hours with the following exceptions;
 - Grade 3 fatigue, asthenia, fever, anorexia, or constipation;
 - Grade 3 nausea, vomiting or diarrhea not requiring tube feeding, total parenteral nutrition, or requiring or prolonging hospitalization;
 - infection, bleeding or other expected direct complication of cytopenias due to active underlying disease;
 - Grade 3 or 4 tumor lysis syndrome (TLS) if it is successfully managed clinically and resolves within 7 days without end-organ damage;
 - Grade 3 or 4 isolated electrolyte abnormalities that last < 72 hours.
- Grade 3 AST, ALT or alkaline phosphatase will be considered dose limiting if it last > 72 hours
- treatment-related deaths are dose limiting
- confirmed Hy's law cases are dose limiting

NOTE: Myelosuppression will not be considered in evaluating toxicity in subjects with acute leukemias or similar advanced myeloid malignancies (MDS, MF) except where bone marrow (BM) hypoplasia occurs for >42 days with BM cellularity <5% in the absence of residual leukemia/disease.

7.4.b RP2D for the combination of AZD1775 with Cytarabine; DLT, MTD and Biological dose

Despite a lack of a clear biomarker/ PD marker for WEE1 kinase inhibition, based on preclinical data an effective pharmacological dose is up to the range of 750 nM, possibly higher to maximally 1000 nM. From recent PK data (REFMAL 984 and NCI study), daily dosing for 5 days for one or two weeks with AZD1775 was determined as the RP2D, that yielded an AUC (0-8 hrs) of ~8000nM. Therefore we would expect that 300mg AZD1775 daily would yield around 600-800 to maximally 1000 nM concentrations of AZD1775 in the first 8 hours.

For the combination arms (Arms A and B) in the Escalation portion we will escalate dose starting at AZD1775 200 mg daily on a 5-2-5 schedule. We will escalate up to/ until

- a) the current MTD/ RP2D of 300 mg daily (5-2-5 schedule) is reached at acceptable toxicity (AEs) regardless of preclinical PK efficacy
- b) DLT defining toxicities/ AEs are observed
- c) clinical efficacy is observed that would meet the primary response endpoint already below the current RP2D of 300 mg AZD1775 daily
- d) Clinical PK (AUC) of AZD1775 reaches approx. > 1000 nm/ hr

We will accomplish above goals with real-time assessment of safety, efficacy, PK and/or PD in each cohort.

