8. To be collected on all patients at baseline. If no baseline marrow samples obtained, the peripheral blood research sample becomes mandatory to participate in study. Bone marrow aspirate specimens must be collected and submitted per section 14.0. If bone marrow performed at end of study as part of patient's standard of care, collect sample per section 14.0.
9. After 2 cycles, CBC frequency may be reduced at treating physician's discretion but needs to be performed at least once per cycle.
10. Progression marrow can be used as EOS marrow if patient is taken off trial based on the results. Additional EOS bone marrow can be omitted if a progression marrow was done, or an EOS marrow can be done at physician discretion and is optional.
11. ≤ 28 days prior to registration; for patients with an outside marrow biopsy within 4 weeks of study start, outside results can serve as baseline after review at NYU.
12. Patient questionnaire booklet must be used; copies are not acceptable for this submission. Booklet should be completed by patient prior to review of treatment response and discussions of patient's general health since last treatment evaluation.
13. For patients at high risk of tumor lysis syndrome (TLSTLS labs will be performed at least twice during the first week of therapy, when maximum TLS risk is highest. . Additional monitoring will be done on a case by case basis.
14. Either conventional cytogenetics or FISH panel (or both based on physician discretion) for AML to be performed at baseline. If diploid cytogenetics at baseline, subsequent cytogenetic studies may be omitted unless disease progression is suspected. For FISH based cytogenetic assessments, an entire AML FISH panel should be performed at baseline, while on subsequent marrows only positive specific FISH abnormalities/probes need to be repeated unless disease progression is suspected, in which case a full AML FISH panel or instead conventional cytogenetics should be performed.
15. Booklets to be completed at end of all cycles.
16. Prior to the start of treatment.
17. ECG in triplicate on day1 of each cycle, for cycle 1, ECGs will be conducted at least weekly.
18. To be tested on C1D1 prior to treatment.
 - A. For AML patients, CBC and blood chemistries will be collected at least twice weekly for Cycle 1
 - B. For AML patients, CBC and blood chemistries will be collected weekly for Cycle 2
 - C. For cycle 1, ECGs will be conducted at least weekly.
 - R. Research funded (see Section 19.0).

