In general, if a patient experiences a G1/G2 non-hematological toxicity, no dose modification is required (except QTc prolongation, see Table 8.31). If a patient experiences a G3 or G4 non-hematological toxicity which is not attributable to the disease or disease related processes under investigation, dosing will be interrupted and/or the dose reduced and

supportive therapy administered as required. Any patient who develops a Grade 3 or 4 non-hematologic toxicity that does not resolve to \leq Grade 1 within 21 days should be removed from the study treatment unless approved by the Medical Monitor and Study Chair.

No more than two dose reductions will be allowed for any patient. Patients requiring further dose reduction due to toxicity must discontinue study treatment. Dose re-escalation is not allowed. If the patient has concurrent neutropenia and thrombocytopenia, please follow the most conservative guidance in the table below and discuss with Medical Monitor as needed.

If haematological parameters do not recover within 21 days, the patient should be removed from the study treatment.

Table 8.31

Electrocardiogram QT corrected interval prolonged	
QTc Value (triplicate)^a	AZD1775
QTc 450-480 ms (males) or 470-480 (females)	Hold. Once QTc interval has returned to pretreatment status and correction of possible electrolyte imbalance has been made, resume at next lower dose level.
QTc 481-500 ms	Hold. Seek cardiologist advice, patient may resume at next lower dose level if cardiologist agrees.
QTc \geq 501 ms	Discontinue treatment. Seek cardiologist advice
Shift from baseline of \geq 60ms	Discontinue treatment. Seek cardiologist advice

Table 8.32

→ → Use the NCI Common Terminology Criteria for Adverse Events (CTCAE) version 5.0* unless otherwise specified ← ←			
CTCAE System/Organ/Class (SOC)	ADVERSE EVENT	AGENT	ACTION**
BASED ON INTERVAL ADVERSE EVENT***			

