	Blood bilirubin increased Grade 4	AZD1775	Omit dose until resolved to ≤ grade 1, then decrease dose by 1 dose level

→ → Use the NCI Common Terminology Criteria for Adverse Events (CTCAE) version 5.0* unless otherwise specified ← ←			
CTCAE System/Organ/Class (SOC)	ADVERSE EVENT	AGENT	ACTION**
		AraC	Continue treatment at Dose level -1once resolved to ≤ Grade 1
	Alanine aminotransferase (ALT) increased and/or Aspartate aminotransferase (AST) increased Grade 3	AZD1775	Omit dose until resolved to ≤ grade 1 or baseline then: 
 • If resolved in ≤ 7 days, then maintain dose level • If resolved in > 7 days, then decrease dose by 1 dose level
		AraC	Continue treatment at next lower dose level
	Alanine aminotransferase (ALT) increased and/or Aspartate aminotransferase (AST) increased Grade 4	AZD1775	Omit dose until resolved to ≤ grade 1 or baseline, then decrease dose by 1 dose level
		AraC	Continue treatment at dose reduced AraC of 10mg s.c. twice daily days 1-5 & 8-12
Cardiac Disorders	Cardiac disorders – Other ≥ Grade 4	AZD1775	Omit dose and discontinue patient from study
Other Non-Hematologic events	Grade 3	AZD1775	Omit drug and follow patient at least weekly or at least every other week until adverse event has resolved to grade ≤ 2, restart drug at next lower dose level. Contact protocol chair and a medical monitor if resumption of AZD1775 at previous dose may be clinically indicated
Other Non-Hematologic events	≥ Grade 4	AZD1775	Omit drug and follow patient at least weekly or at least every other week until adverse event has resolved to grade ≤ 2, restart drug at next lower dose level. For a repeated Grade 4 event discontinue patient from study
AT TIME OF RETREATMENT (at beginning of each next cycle)			
Non Hematologic	All Non-Hematologic Toxicities Grade ≥ 4 (With the exception of nausea, vomiting or diarrhea controlled with appropriate medications.)	AZD1775	Hold AZD1775 and AraC. Re-check patient weekly or at least every other week. When event returns to ≤ grade 2, resume AZD1775 and/ or AraC treatment at next lower dose level. For a repeated Grade 4 event present/ recurred at beginning of each next cycle patient will be discontinued from therapy.

* Located at http://ctep.cancer.gov/protocolDevelopment/electronic_applications.ctc.htm

** Use the following to describe actions in the Action column:

- Omit = Treatment is not given for the day that is omitted, but treatment may resume once the adverse

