event has resolved as mandated in Table 8.2. For example, if treatment is omitted on Day 8, but the adverse event has resolved by Day 10, treatment may resume on Day 10 to complete the cycle. Missed doses will not be made up.

- Hold/Delay = Treatment can be made up as part of this cycle
- Discontinue = Treatment is totally stopped

***AraC can be continued each cycle regardless of dose hold or adjustments for AZD1775, if patient is presumed to derive clinical benefit from the intervention.

Patients whose treatment is interrupted or permanently discontinued due to an adverse event including abnormal laboratory values must be followed by their treating physician as clinically indicated.

The maximum time allowed for treatment interruption due to toxicity is 4 weeks from the intended dosing day for the combination arms (Arm A and B) and 3 weeks for the single agent AZD1775 arm (Arm C). If interruption is > 4 and 3 weeks for Arms A, B and C respectively, continuation of treatment may be allowed on a case by case basis (i.e. clinical benefit) as determined by the treating physician in discussions with the Medical Monitor (NYU DSMC) and the Stuyd Chair. However, any discontinued patient will continue to be followed for toxicity. Dose interruptions should be reported on the appropriate Dosage Administration CRF.

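### The DLT definition in 7.4a has no criterion for drug-related toxicity that permanently ends AZD1775, so some cycle-1 stops drop out of the counts that clear a dose

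*Combined protocol and SAP*

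**What the plan says.** **DLT definition (7.4a).** The window is cycle 1. A toxicity of Grade 3 or higher that is not clearly due to the leukemia is a DLT unless it falls to at most "Grade 2 within 24 hours with the following exceptions" listed after it (for example tumor lysis syndrome and isolated electrolyte abnormalities). Two outcomes count whatever their duration: "treatment-related deaths are dose limiting", and so are confirmed Hy's law cases. Grade 3 liver enzymes have a 72-hour window. Myelosuppression is set aside except for prolonged marrow hypoplasia. No item refers to stopping the drug.

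**Discontinuation rows (Section 8).**
- Table 8.31, QTc of 501 ms or more: "Discontinue treatment. Seek cardiologist advice". The row beginning "Shift from baseline of" and set at 60 ms or more has the same action.
- Table 8.32, Cardiac disorders - Other, Grade 4 or higher: "Omit dose and discontinue patient from study".
- The notes to Table 8.32 define the term: "Discontinue = Treatment is totally stopped".

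None of these rows has a duration condition. The opening of Section 8.0 describes the dose modifications as general guidelines, subject to the treating physician's judgement.

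**Replacement.** Under 7.55 and 13.4, a patient who does not complete the cycle (28 days in 13.4) for a reason other than a DLT is non-informative and another is treated. Section 13.4 adds that all toxicity information is still used in the analysis.

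**Counts.** Sections 7.53 and 16.7 clear a dose at no more than 1 DLT in 6 patients. Section 16.8 monitors with the same DLT definition.

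**The concern.** Section 8 judges certain toxicities serious enough to end AZD1775 for the patient. Section 7.4a asks a different question: how high was the grade, and did it persist? An event can satisfy the first and fail the second. The rule that decides whether the dose goes forward then sees nothing, or sees a replacement patient instead.

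The cleared dose goes to every expansion patient in the arm. QTc prolongation is a listed adverse reaction to AZD1775 monotherapy (1.41), so the QTc rows are not hypothetical for this drug.

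**Working it through.** **1. How an event goes uncounted.**

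| Event in cycle 1 | Section 8 action | 7.4a result |
|---|---|---|
| Cardiac disorders - Other, Grade 4, at most Grade 2 within 24 h | discontinue | not a DLT (duration) |
| QTc row met, Grade 3 or higher, at most Grade 2 within 24 h | discontinue | not a DLT (duration) |
| QTc row met, graded below 3 | discontinue | not a DLT (grade), however long it lasts |
| Any of these rows, Grade 3 or higher, persisting beyond 24 h | discontinue | DLT, if no listed exception applies |

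Table 8.31 is in milliseconds and the documents give no conversion to grades, so the second and third lines must both be kept open.

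An uncounted patient is replaced if the cycle is not completed. If the stop follows the last AZD1775 dose on day 12, or AraC continues in Arms A or B as the notes to Table 8.32 allow, the patient may instead stay in the denominator as DLT-free. Either way the event adds nothing to the numerator.

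**2. The plan's own figures.** Section 16.8 uses P(rate > 0.20) under Beta(1 + x, 1 + n - x). For 2/6, 3/9, 4/12, 5/15, 6/18 and 6/21 this gives 0.852, 0.879, 0.901, 0.918, 0.932 and 0.867, matching the printed 0.85, 0.88, 0.90, 0.92, 0.93 and 0.87.

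**3. One cohort.** Six patients are treated, with one DLT and one uncounted stop.
- Replaced: 1 of 5 informative. A replacement who is DLT-free (probability about 0.80 at a true DLT rate of 20%) makes it 1 of 6. The dose is cleared, with 16.8 posterior Beta(2,6) = 0.577.
- Counted: 2 of 6. The MTD is exceeded under 7.53, and the posterior Beta(3,5) = 0.852 is above the 0.80 limit.

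This configuration is itself uncommon. Its probability is 30 × 0.20 × q × (0.80 - q)^4, where q is the rate of uncounted stops: 0.023 at q = 1% and 0.044 at q = 2%.

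**4. Average effect.** Let d be the true DLT rate under 7.4a, with q disjoint from d. Both are assumptions, because the documents give neither. The chance of clearing a dose is P(X ≤ 1), X ~ Bin(6, p), with p = d/(1 - q) if replaced, p = d + q if counted, and p = d if kept as DLT-free.

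| d | q | replaced | counted | fall |
|---|---|---|---|---|
| 0.20 | 0.01 | 0.650 | 0.631 | 0.020 |
| 0.20 | 0.02 | 0.645 | 0.606 | 0.039 |
| 0.10 | 0.01 / 0.02 | | | 0.018 / 0.037 |
| 0.30 | 0.01 / 0.02 | | | 0.015 / 0.029 |

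If every such patient were kept as DLT-free, clearing at d = 0.20 is 0.655, and the falls become 0.025 and 0.049.

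Escalation after 0 of 3 (7.21, Arms A and B) is (1 - p)^3. At d = 0.20, replaced against counted, it is 0.508 against 0.493 (q = 1%) and 0.504 against 0.475 (q = 2%).

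**The case against.** The best defence is that individual stopping rules and dose-level DLTs answer different questions, and 7.4a consistently uses persistence windows (24 hours, 72 hours, 7 days, 42 days). That is a coherent choice for events after which dosing can resume. It is weaker where Section 8 says dosing should not resume, and 7.4a already sets duration aside for deaths and Hy's law.

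Several stronger readings are tempting, and the documents do not support them:
- *The toxicity is discarded.* It is not. Section 13.4 keeps it for analysis, 16.41 tabulates the maximum grade of each event per patient, and SAE and DSMC review would see it. These do not change the DLT count.
- *The plan makes the stops mandatory.* Section 8.0 calls its actions general guidelines.
- *The 24-hour rule is the sole cause.* A QTc event graded below 3 is missed on grade, not duration.
- *Sparse ECGs let events escape.* Table 4.1 has "ECG in triplicate on day1 of each cycle, for cycle 1, ECGs will be conducted at least weekly". Without a repeat tracing, resolution within 24 hours is not shown, so the natural reading counts a Grade 3 or higher event. The schedule favours counting.
- *Replacement is automatic.* It is not, for the reasons in step 1 of the check.
- *The other non-hematologic row of Table 8.32 belongs here too* ("For a repeated Grade 4 event discontinue patient from study"). An uncounted case needs two Grade 4 events in cycle 1, each settling quickly, with the second at a reduced dose. Counting it would charge that event to the wrong dose and could conflict with the electrolyte and tumor lysis exceptions. It is left out.

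**Conclusion.** The gap is real and small. A cycle-1 toxicity related to AZD1775 that meets one of three discontinuation rows can be absent from the counts that clear a dose, because of quick resolution or, for QTc, because of grade. The loss is about 2 to 4 percentage points in the chance of clearing a dose at a 20% DLT rate. That rests on an assumed frequency of 1-2% and on independent patients. In a single cohort, one such event can change the decision.

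A reader might infer that the plan conceals toxicity or that the escalation is unsafe. The documents do not support this: the data are retained and reviewed, and AZD1775 is capped at 300 mg. This is a cheap improvement, not a design failure.

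**What to change.** Add to 7.4a: *Subject to the listed exceptions, a cycle-1 non-hematologic adverse event at least possibly related to AZD1775 and not clearly due to underlying disease, for which AZD1775 is permanently discontinued under Table 8.31 (QTc 501 ms or more, or shift of 60 ms or more) or Table 8.32 (Cardiac disorders - Other, Grade 4 or higher), is a DLT regardless of time to resolution.*

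State in 7.55 and 13.4 that such patients count as DLTs and are not replaced. Leave the replacement rule as it is for all other stops. Sections 16.7 and 16.8 then follow the amended definition.

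The cost is one sentence and two clauses, with no new visits, tests or patients. There are two downsides. A dose is cleared slightly less often, by the amounts shown above. A transient shift of 60 ms or more with an absolute QTc below 501 ms would also count as a DLT when AZD1775 is stopped for it. For example, a rise from 380 to 440 ms would qualify although 440 ms is within the eligibility limits. The sponsor should accept that second consequence knowingly.

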Appendix IX – Childbearing Potential & Contraception

Schema

If a patient is deemed ineligible or a does not start first dose of treatment, please refer to Section 13.0 for follow-up information.

Cycle length=28 days

NOTE: The Safety portion of this trial will monitor six patients in each arm (combination and single agent) and observe them for a minimum of 28 days to assess toxicities.

Primary & Secondary MF: Primary Myelofibrosis (PMF) and Secondary MF after Polycythemia Vera (PV) and Essential Thrombocytosis (ET) (post-PV/ post-ET MF)

Generic name: AZD1775, Adavosertib Brand name(s): n/a Availability: Provided by AstraZeneca
	
Generic name: Cytosine arabinoside Brand name(s): Cytosar, ® Availability: Commercially available

--	--

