7.2 Treatment Plan for AZD1775 combined with AraC (Arms A and B)

7.21 Safety Portion

The safety portion of this trial will consist of a limited dose escalation and subsequently assess the safe combination dose of AZD1775 with standard AraC s.c. twice daily dosing. A limited safety run in dose escalation of AZD1775 will be performed as outlined in Table 7.21. Three subjects from either arm will be treated and observed for a minimum of 28 days to assess toxicities. Toxicity and DLT/MTD criteria will follow a classical three by three dose escalation toxicity assessment:

In the run-in portion of the trial, 3 patients who are eligible for the trial will be treated at dose level 0 (AZD1775 200 mg PO once daily and AraC 20 mg s.c. twice daily days 1-5 & 8-12) and observed for a minimum of 28 days. If there are no DLT defining toxicities, the following 3 patients will be treated at dose level 1 (AZD1775 250 mg PO once daily and AraC 20 mg s.c. twice daily days 1-5 & 8-12). If there are no DLT defining toxicities at dose level 1, the next 3 will be treated at dose level 2 (AZD1775 300 mg PO once daily and AraC 20 mg s.c. twice daily days 1-5 & 8-12). If there are no DLTs in the first 3 patients at dose level 2, an additional 3 patients will be treated. If $\leq 1/6$ patients at dose level 2 experience DLT, the Expansion portion (cohort) of the trial will be opened for the remaining patients.

If 1/3 patient experiences a DLT at a given dose level, an additional 3 patients will be enrolled at this dose level. If there are no further DLTs (maximum of $\leq 1/6$ patients with DLT at any given dose level) this dose level will be defined as the MTD dose level and advanced to the Expansion portion of the study. If 2/3 patients experience a DLT, dose will be de-escalated by one dose level and an (additional) 3 patients treated at the next lower dose level, unless six patients have been treated already and there were $\leq 1/6$ DLT, then this level will be defined as MTD dose level and advanced to the Expansion portion. If $\geq 2/6$ patients experience at any dose level, then enrollment into that study arm will be placed on hold, and a meeting of all participating investigators, the NYU DSMC Medical Monitor, the Astra Zeneca Trial/ Program Lead will be called to determine how best to proceed, as well as available PK data will be reviewed.

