7.5 MTD Determination

This MTD determination applies to the Safety Portion. MTD for the safety portion will be defined as the dose level below the lowest dose that induces dose-limiting toxicity in at least one-third of subjects (at least 2 of a maximum of 6 subjects).

- 7.51 Three subjects will be treated at a given dose level combination and observed for one cycle to assess toxicity (accrual will be suspended while the 3 subjects are treated and observed – only applicable to the dose escalation cohort/ part of study).
 - 7.52 If DLT is not seen in any of the 3 subjects or in 1 of 3 subjects, 3 new subjects will be accrued and treated at the same dose level (accrual will be suspended while the 3 subjects are treated and observed). If DLT is seen in 2 or 3 of 3 subjects treated at a given dose level, then the next 3 subjects will be treated at the next lower dose level, if only 3 subjects were enrolled and treated at this lower dose level.
 - 7.53 After enrolling 6 subjects on a specific dose level, if DLT is observed in 1 or less subjects, then the combination dose will be considered safe for the expansion phase. If DLT is observed in at least 2 of 6 subjects, then the MTD will have been exceeded and defined as the previous dose unless only 3 subjects were treated at the lower dose level. In that case, 3 additional subjects will be treated at this lower dose level.
 - 7.55 If a subject fails to complete one cycle of treatment for reasons other than dose-limiting toxicity defined adverse events, the subject will be regarded as non-informative for estimating the MTD and an additional subject will be treated at the current dose level.
- 7.6 Dose escalation (inpatient) will not be allowed for a subject.
- 7.7a For this protocol, the subject must return to the consenting institution for evaluation at least once per cycle.
- 7.7b Local Medical Doctor (LMD)
When it has been determined that a patient's malignant disease is stable or objective tumor regression has been observed and the patient is tolerating therapy without excessive toxicity, after the first cycle of treatment, the standard of care drug AraC may be administered by the patient's Local Medical Doctor

(LMD). However, study drug AZD1775 can only be dispensed by an investigator or investigational site of the study. The registering physician retains responsibility for the patient.

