16.7 Early Safety Analysis

An early safety analysis will be performed after 6 patients have been accrued to each arm of the study and observed for one cycle. Accrual will be temporarily halted while these patients are evaluated. If 2 or more of the first 6 patients experience a DLT, as defined below, then the dose level will be reduced as defined in Section 8.0 and another six patients will be treated. If $< 2/6$ patients experience toxicities defined as DLT, then this dose level will be defined as the operational MTD and moved into the expansion portion. Further dose de-escalation to dose level -2 will follow the same guidelines.

Should additional modification be necessary, the study will be closed and evaluated by the study team regarding continuation. Upon determination of the safe dose level, the study will re-open for accrual.

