16.8 Ongoing Safety Analysis

Ongoing safety monitoring will occur continuously; patient-level unacceptable toxicity will be defined as per DLT criteria (Section 7.4) and we will require a toxicity rate of no more than 20%. Monitoring for toxicity will follow a Bayesian-based rule for the probability that the unacceptable toxicity rate exceeds a maximal tolerated level of 20%. We will use a flat Beta(1,1) prior. Early termination for toxicity will be based on a posterior probability above 80% (in parentheses) that the toxicity rate exceeds 20%. Termination will be considered if DLT occurs in: 2 of 6 patients (0.85), 3 of 9 patients (0.88), 4 of 12 patients (0.90), 5 of 15 patients (0.92), 6 of 18 patients (0.93), or 6 of 21 patients (0.87).

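### The only myelosuppression DLT takes more than 42 days to establish, yet dose decisions are allowed after 28 or 21 days and nothing requires a wait

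*Combined protocol and SAP*

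**What the plan says.** Section 7.4a sets the counting window: "DLT is defined as an adverse event occurring during the first cycle of treatment". Its closing note removes myelosuppression from the assessment, with one exception: "except where bone marrow (BM) hypoplasia occurs for >42 days with BM cellularity <5% in the absence of residual leukemia/disease".

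The timing of dose decisions is set in several places:

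- Section 7.21 (Arms A and B): "Three subjects from either arm will be treated and observed for a minimum of 28 days to assess toxicities".
- Section 7.31 (Arm C): "observe them for a minimum of 21 days to assess toxicities".
- Section 7.51: "Three subjects will be treated at a given dose level combination and observed for one cycle to assess toxicity".
- Section 16.7: "An early safety analysis will be performed after 6 patients have been accrued to each arm of the study and observed for one cycle".
- The Schema note, for the combination and single-agent arms alike: "observe them for a minimum of 28 days to assess toxicities". Section 13.4 also uses 28 days.

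Sections 7.22 and 7.32 open expansion as soon as the safety portion is complete. The continuous Bayesian rule in Section 16.8 takes its toxicity definition from Section 7.4.

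**The concern.** Prolonged disease-free marrow hypoplasia is the one myelosuppressive event that the plan chose to treat as dose limiting. The choice is reasonable: Section 1.41 lists anaemia, neutropenia and thrombocytopenia as AZD1775 reactions, and Section 15.27 describes AraC as strongly myelosuppressive. The event's duration threshold, however, is longer than either observation window. A cohort can therefore be cleared before this criterion could have been scored in its most recently treated patient.

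One event can change a decision. Under 7.21, 0/3 escalates while 1/3 enlarges the cohort. Under 7.53, one DLT in six is accepted while two in six exceed the MTD.

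**Working it through.** The plan gives no figure on this point, so the check is a timeline.

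**Earliest scoring day.** Hypoplasia starting on day d first exceeds 42 days on day d + 42.

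- Onset day 1: day 43.
- Onset on the last day of cycle 1: 28 + 42 = day 70 in A/B; 21 + 42 = day 63 in C.

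**Gap after the permitted decision, for the last patient in a cohort.**

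| Arm | Minimum window | Onset day 1 | Onset on last day of cycle 1 |
|---|---|---|---|
| A/B | 28 | 43 − 28 = 15 days | 70 − 28 = 42 days |
| C, by 7.31 | 21 | 43 − 21 = 22 days | 63 − 21 = 42 days |
| C, by Schema and 13.4 | 28 | 43 − 28 = 15 days | 63 − 28 = 35 days |

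**Strict reading (the event must be complete within cycle 1).** Cycle 1 must run past day 42.

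- A/B: 28 + 21 = day 49 under the 21-day haematologic recovery limit in 8.3, or 28 + 28 = day 56 under the general 4-week interruption limit. Either is long enough if a delay occurs.
- C: both limits are 21 days, and 21 + 21 = day 42. That is not enough without a case-by-case extension.
- Whether low counts alone delay cycle 2 is unclear. Section 8.2 exempts them but also points to Table 8.32, which omits AZD1775 for grade 4 counts only in patients with adequate baseline counts.

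**Onset reading (onset in cycle 1, confirmed later).** Section 10.2 follows events to resolution or stabilization, which makes this the more natural reading. Section 16.8 can then count the event, but possibly only after the gap shown above.

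**What one late event does under 16.8.** With a Beta(1,1) prior, P(rate > 0.20 | x of n) = P(Bin(n + 1, 0.20) ≤ x).

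- 2 of 6: 0.8^7 + 7(0.2)(0.8^6) + 21(0.2^2)(0.8^5) = 0.210 + 0.367 + 0.275 = 0.852. This reproduces the plan's 0.85.
- 1 of 6: 0.210 + 0.367 = 0.577.

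One late-confirmed DLT would move a cohort with 1 of 6 from well below the 0.80 threshold to above it.

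**Patients who could enter during the gap.** Assume the planned 2-4 patients a month (16.3), split by planned arm size (A/B 45/67, C 22/67), and a 30.4-day month.

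- A/B: 1.34-2.69 a month. Over 15 days, 0.66-1.33 patients; over 42 days, 1.85-3.71.
- C: 0.66-1.31 a month. Over 22 days, 0.48-0.95 patients; over 42 days, 0.91-1.81.

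**Detection.** The criterion needs marrow cellularity. A marrow after cycle 1 is discretionary in AML (Table 4.1, footnote 3) and unscheduled at that time in MDS and MF (Tables 4.2 and 4.3). The first fixed one is at the end of cycle 2, nominally day 56 in A/B and day 42 in C. All three tables also call for a marrow at suspected CR/CRi.

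**The case against.** Several counter-arguments have force.

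- **The windows are minimums.** A longer wait is allowed. That stands, but none is required, and 7.51 and 16.7 set the trigger at one cycle. Section 1.51 says that AraC cycles often last 4-6 weeks and that the toxicity criteria will reflect this. That may explain the 42-day threshold, but even a 42-day cycle falls one day short.
- **Staggered entry narrows the gap.** At the planned accrual, A/B patients arrive 11.3-22.6 days apart. When the third reaches day 28, the first is at about day 51-73 and the second at about day 39-51. The largest gap therefore applies to the last patient. This reduces the problem without removing it, especially for late onset.
- **Marrow may be done anyway.** A patient whose disease appears cleared but whose counts stay low may well be a suspected CRi, and that calls for a marrow. So a reader should not infer that the event would go undetected; it is only that detection before the decision is not assured.
- **Other DLTs cover much of the harm.** Treatment-related deaths count. Complications of cytopenia are exempt only when due to active underlying disease. For the combination arms, 7.4b promises real-time safety review.

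A reader might also infer that the criterion can never be met, or that Arm C is escalated too early. The documents support neither. A delay can lengthen cycle 1 in A/B, and the onset reading lets the event count later. Arm C starts at 300 mg and can only stay there or come down.

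**Conclusion.** The concern holds as a mismatch between the criterion and its window. The sole myelosuppression DLT cannot be scored before day 43, decisions are permitted from day 28 or day 21, and no text requires a wait or says that later confirmation counts. Under the strict reading it counts only after a toxicity delay. Under the onset reading the defect is a lag, for the last patient in a cohort, of 15-42 days in A/B and 22-42 days in C (15-35 if the 28-day window applies). The lag affects escalation in A/B and the opening of expansion in every arm.

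The day counts assume onset on or after day 1. It is tempting to attach a probability of wrongly clearing a dose. The documents give no rate of disease-free hypoplasia and no basis for treating it as independent of the other DLTs, so that size is unknown. The harm is limited by the other DLT criteria, but the gap is worth closing.

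The Arm C window of 21 days in 7.31 against 28 days in the Schema and 13.4 is a separate inconsistency. Both values fall short of day 43.

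**What to change.** 1. In 7.4a, state that marrow hypoplasia with onset in cycle 1 is a DLT when it later meets the >42-day criterion.
2. In 7.5, 16.7 and 16.8, state that a late-confirmed DLT is added to the count for its dose level and that the MTD and stopping rules are then re-applied. Hold a cohort's decision only for a patient whose end-of-cycle-1 marrow, already done as scheduled or clinically indicated, shows cellularity below 5% without residual disease.
3. State one Arm C observation window, 21 or 28 days, in the Schema, 7.31 and 13.4.

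These are wording changes with no added procedures. The downside is a hold of up to about 6 weeks (42 days) for a cohort with such a patient. Tying the hold to an existing marrow finding matters. Table 8.32 expects prolonged neutropenia in this population, so a hold on suspicion alone would have no clear trigger and could be frequent.
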